$$Y_{ijklm} = \mu + \tau_j + \varphi_k + \alpha_l + \gamma_m + \lambda_{lm} + \beta \cdot \text{baseline tTG IgA}_{ijklm} + \eta_i + \varepsilon_{ijklm}$$

where

Y_{ijklm} is the relative (%) change from baseline in anti-tTG IgA result for subject i ($i = 1, \dots, n_{jkl}$) from site j ($j = 1, 2, 3$), sex k ($k = 1, 2$) and treatment group l ($l = 1, 2, 3$) at visit m ($m = 3, 5, 7, 8$),

μ is the overall mean,

α_l is the fixed effect due to treatment l ,

φ_k is the fixed effect due to sex k ,

τ_j is the fixed effect due to site j ,

γ_m is the fixed effect due to time point m ,

λ_{lm} is the fixed interaction effect due to treatment l and time point m ,

β is the parameter estimate of the baseline anti-tTG IgA result,

η_i is the random effect due to subject i ,

ε_{ijklm} is the random error for subject i from site j ($j = 1, 2, 3$), sex k ($k = 1, 2$) and treatment group l for time point m .

Due to the repeated structure of the data, the measurements within a subject will be correlated. Therefore, it is assumed that the overall covariance matrix of the response is block-diagonal. In order to determine the covariance structure that best fits the data, the same model with different covariance structures is fitted. Initially, models will be fit

assuming unstructured (UN) variance-covariance structure. Common within and between treatment variance components (compound symmetry (CS), first-order autoregressive (AR(1)) and Toeplitz covariance structures) will be further explored to increase sensitivity of statistical tests. The best model will be chosen by comparing the Akaike Information Criterion (AIC) of the models with different covariance structures.

The following SAS program will be used for carrying out the analysis:

```
proc glimmix data=ttgiga;
  class subjid trt site sex time(ref=FIRST);
  model ttgiga = ttgiga.bl trt site sex time trt*time / solution;
  random _residual_ / subject=subjid type=UN;
  estimate "150 mg AMG 714 vs Placebo" trt 1 0 -1 /alpha=0.05 cl;
  estimate "300 mg AMG 714 vs Placebo" trt 0 1 -1 /alpha=0.05 cl;
  estimate "Visit 3: 150 mg AMG 714 vs Placebo" trt 1 0 -1
    trt*time 0 0 0 1
    0 0 0 0
    0 0 0 -1 /alpha=0.05 cl;
  estimate "Visit 3: 300 mg AMG 714 vs Placebo" trt 0 1 -1
    trt*time 0 0 0 0
    0 0 0 1
    0 0 0 -1 /alpha=0.05 cl;
  estimate "Visit 5: 150 mg AMG 714 vs Placebo" trt 1 0 -1
    trt*time 1 0 0 0
    0 0 0 0
    -1 0 0 0 /alpha=0.05 cl;
  ...

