  estimate "Visit 8: 300 mg AMG 714 vs Placebo" trt 0 1 -1
    trt*time 0 0 0 0
    0 0 1 0
    0 0 -1 0 /alpha=0.05 cl;
  lsmeans trt /alpha=0.05 cl;
  lsmeans trt*time /alpha=0.05 cl;
  ods output CovParms=Cov_Par LSMeans=LS_est Estimates=Eff_est
    FitStatistics=Fit_Stat ParameterEstimates=Par_est
    Tests3=Type_3;
run;
```

Note that the value of `type` will be changed according to which covariance structure is being fitted.

The modelling results (parameter estimates, covariance parameter estimates, estimated treatment effect, marginal means estimates and results of the check of assumptions, e.g. the normality assumption) will be tabulated and 95% confidence intervals added, where appropriate. If the parametric assumptions are not met, then in addition to the above-specified model, a generalized estimating equation (GEE) approach will be used as well.

As a secondary approach, the same model will be fitted using the absolute change in anti-tTG IgA density as a response variable. Modelling results (parameter estimates, covariance parameter estimates, estimated treatment effect, marginal means estimates and results of the check of assumptions, e.g. the normality assumption) will be tabulated and 95% confidence

intervals added, where appropriate. If the parametric assumptions are not met, then in addition to the above-specified model, a generalized estimating equation (GEE) approach will be used as well.

The baseline and post-baseline anti-tTG IgA results along with the change from baseline values (both relative and absolute) will also be described by summary statistics and tabulated by treatment group. Anti-tTG IgA results will also be listed. Individual and mean anti-tTG IgA results, will also be presented graphically by time point and treatment group.

PP populations will be used for the analysis.

Attenuation of gluten-induced serum antibodies: anti-deamidated gliadin peptide antibodies (anti-DGP) IgA and IgG

Anti-deamidated gliadin peptide antibodies (anti-DGP), IgA or IgG, may be positive in some patients with celiac disease who are negative for anti-tTG, due to their different kinetics and to the possibility of IgA deficiency, in which case, DGP IgG are the most reliable antibodies (Brusca, 2015).

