The total weekly bowel movement counts will be analysed using generalized linear mixed models with subject as a random effect. The statistical model will include as fixed effects treatment group, sex, site, time (week) and time point-by-treatment group interaction. Poisson distribution with log-link will be used for modelling the counts. The following model will be fitted:

$$\log(Y_{ijklm}) = \mu + \tau_j + \varphi_k + \alpha_l + \gamma_m + \lambda_{lm} + \eta_i + \varepsilon_{ijklm},$$

where

Y_{ijklm} is the total bowel movement count for subject i ($i = 1, \dots, n_l$) from site j ($j = 1, 2, 3$), sex k ($k = 1, 2$) and treatment group l ($l = 1, 2, 3$) at visit m ($m = 3, 5, 7, 8$),

treatment group l ($l = 1, 2, 3$) at week m ($m = 0, 1, \dots, 16$),

μ is the overall mean on log-scale,

α_l is the fixed effect due to treatment l on log-scale,

φ_k is the fixed effect due to sex k on log-scale,

τ_j is the fixed effect due to site j on log-scale, γ_m is the fixed effect due to week m on log-scale,

λ_{lm} is the fixed interaction effect due to treatment l and week m on log-scale,

η_i is the random effect due to subject i ,

ε_{ijklm} is the random error for subject i from treatment group l for week m .

Due to the repeated structure of the data, the measurements within a subject will be correlated. Therefore, it is assumed that the overall covariance matrix of the response is block-diagonal. In order to determine the covariance structure that best fits the data, the same model with different covariance structures will be fitted. Initially, models will be fit assuming unstructured (UN) variance-covariance structure. Common within and between treatment variance components (compound symmetry (CS), first-order autoregressive (AR(1)) and Toeplitz covariance structures) will be further explored to increase sensitivity

of statistical tests. The best model will be chosen by comparing the Akaike Information Criterion (AIC) of the models with different covariance structures.

The following SAS code will be used to fit the above-specified model:

```

proc glimmix data=bsfs ic=q;
  class subjid trt sex site week(ref=FIRST);
  model bsfs = trt sex site week trt*week / solution dist=POISSON;
  random _residual_ / subject=subjid type=UN;
  estimate "150 mg AMG 714 vs Placebo" trt 1 0 -1 /alpha=0.05 cl ilink;
  estimate "300 mg AMG 714 vs Placebo" trt 0 1 -1 /alpha=0.05 cl ilink;
  estimate "Week 0: 150 mg AMG 714 vs Placebo" trt 1 0 -1

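### The repeated-measures code has no visit, week or day index on the residual side, so a skipped record without a placeholder row can misplace later records and distort standard errors in either direction

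*SAP*

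**What the plan says.** In SAP 7.6.2 the anti-tTG IgA program puts the visit variable in the CLASS list ("class subjid trt site sex time(ref=FIRST") and in the fixed effects ("trt site sex time trt*time / solution"). The residual statement, "random _residual_ / subject=subjid type=UN", leaves it out. The anti-DGP, GSRS and CeD-GSRS programs repeat that statement. So does BSFS, where week is a class variable ("class subjid trt sex site week(ref=FIRST") but again is not in the residual statement. Both CeD PRO programs in 7.7.4 have the same form with AR(1).

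The prose intends a correlation structure defined over time points. In 7.6.2 the models start "assuming unstructured (UN) variance-covariance structure", then try "compound symmetry (CS), first-order autoregressive (AR(1)) and Toeplitz covariance structures", and "The best model will be chosen by comparing the Akaike Information Criterion (AIC" is the selection rule. The only change announced for the residual statement is its type: "Note that the value of `type` will be changed according to which covariance structure is being fitted".

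Nothing in the SAP says that a missed visit or diary week is kept as an empty row. Carry-forward in 7.2.2 is limited to biopsy variables, so antibody and diary gaps are not filled.

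**The concern.** With no time effect in the residual statement, the program knows only that a record is the first, second or third for its subject. UN, AR(1) and Toeplitz all give meaning to position. A subject seen at Visits 3, 7 and 8 but not 5, with no row for Visit 5, has Visit 7 treated as the second time point and Visit 8 as the third. The fixed effects still label the visits correctly, so no visit mean is attached to the wrong visit, but the weights and standard errors come from a covariance matrix that mixes time points. The four structures are compared by AIC on the same misplaced records, so that choice can be distorted too. At stake are the confidence intervals and p-values of the antibody and symptom contrasts, and nothing in the tabulated results would reveal the error.

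**Working it through.** **Figures in the SAP.** None bears on this point. The sample size used below is that of section 6: 17 evaluable per arm, and 17/(1 − 0.19) = 20.99, which reproduces the stated 21 per arm.

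**Which gaps shift records.** The antibody models use Visits 3, 5, 7 and 8 (correct slots 1, 2, 3, 4). With absent rows and record-order placement:

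| Missing visit | Slots given to the observed visits | Shift? |
|---|---|---|
| 3 | 5→1, 7→2, 8→3 | all three |
| 5 | 3→1, 7→2, 8→3 | two |
| 7 | 3→1, 5→2, 8→3 | one |
| 8 | 3→1, 5→2, 7→3 | none |

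**How a slot is contaminated.** Assume SD 1:1.5:2:2 over the four visits and 5% independent skips at Visits 3 and 5. Slot 1 should have variance 1. It receives 0.95 × 1 + 0.05 × (0.95 × 1.5² + 0.05 × 2²) = 0.95 + 0.05 × 2.3375 = 1.067, an SD of 1.033.

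**Effect on standard errors (large-sample).** Fit the unstructured matrix V by likelihood, with records placed (a) by visit or (b) by order. For missingness pattern p with weight w, visit-selection matrix Z, true covariance S and fitted block V:

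- A = Σ w Z′V⁻¹Z and B = Σ w Z′V⁻¹SV⁻¹Z
- reported variance ∝ A⁻¹; true variance ∝ A⁻¹BA⁻¹
- The factor 2/17 for a two-arm contrast cancels in the ratio.

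Assumptions, none of them from the SAP: AR-type correlation 0.6, skips completely at random, skipped rows absent. The table gives reported/true SE, as the range over the four visit contrasts and their average.

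| SD over visits | 5% skips at Visits 3 and 5 | 10% at all visits | Only Visit 8 missing |
|---|---|---|---|
| flat | 0.99-1.00 | 0.99-1.00 | 1.000 |
| 1:1.5:2:2 | 0.92-1.01 | 0.88-1.03 | 1.000 |
| 1:2:3:3 | 0.83-1.00 | 0.77-1.04 | 1.000 |

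With placement by visit, every ratio is 1.000.

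**In terms of a nominal 5% test**, using 2{1 − Φ(1.96 × ratio)}:

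- 0.88: 1.96 × 0.88 = 1.725, giving 8.5%.
- 0.77: 1.96 × 0.77 = 1.509, giving 13%.
- 1.04: 1.96 × 1.04 = 2.038, giving 4.2%.

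**Sensitivity.** With correlation 0.5 or 0.8 and 15% skips at each of the first three visits, ratios were 0.757-1.095 for another rising SD pattern, 0.889-1.032 for falling SD, 0.715-1.094 for humped SD and 0.984-0.999 for flat SD. When the true structure is compound symmetric the ratio is 1.000, whether UN or CS is fitted.

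**Small-sample check.** In 250 simulated trials per setting (17 per arm, 10% of visits missing, correlation 0.6), SD 1:2:3:3 gave type I error of 10-15% against 5-8% when aligned. SD 1:1.5:2:2 gave 4-12% against 4-7%. Monte Carlo error is about 2 points, so the second comparison is not conclusive.

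**Longer series.** For AR(1) over 16 weeks with flat SD, correlation 0.6-0.9 and 10-20% random gaps, single-week SEs were about 1-6% too small and the all-week average at most 1%. For daily AR(1) the error was at most about 2%, even at 30% gaps.

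**The case against.** The strongest reply is that the trigger is assumed. The SAP does not say that rows for missed visits are absent, and the count of missing observations promised by visit in 7.2 fits datasets that hold a row for each. That is a fair hint, but it is no requirement on the modelling datasets, and the code is safe only if they keep such rows.

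Second, these analyses use the PP sets, which need a second biopsy. The exit biopsy falls close to Visit 7, and Visits 3 and 5 are dosing visits, so intermittent antibody gaps may be few. This stands as a reason to look first at the 5% column. It does not rule gaps out: 7.1 foresees missed doses, and 7.2.1 provides for a missing Week 0 score.

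Third, UN is an unlikely choice for GSRS and CeD-GSRS. Sixteen weeks need 16 × 17/2 = 136 covariance parameters, against 2 for CS, so AIC would prefer UN only if −2 log L fell by more than 2 × 134 = 268, with about 51 subjects. This too stands. The large ratios belong to the antibody models.

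Fourth, the prose intends the right structure, and a note in 7.6.1 lets code be modified without an SAP amendment. That makes the correction easy, but it does not correct a program the SAP says will be used.

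A reader might go further and infer that standard errors will be too small, or that the antibody findings will be falsely positive. The SAP supports neither. It gives no skip rate and no covariance, some contrasts had standard errors that were too large, and with flat SD the error was under 2%.

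**Conclusion.** The omission is plain in the text and occurs in every repeated-measures program. Its consequence is conditional. It needs a gap before a later observed record, no placeholder row, and a position-dependent structure. Where those hold, standard errors and the AIC comparison can be wrong in either direction, with standard errors more often too small. For the four-visit UN antibody models at 5-10% skips, the reported SE is within about 1% of the true one if SD is flat, but can be up to 12% too small if SD rises 1:1.5:2:2 and up to 23% too small if it rises 1:2:3:3. At the other end it is up to 3% and 4% too large. Those SD patterns, the skip rates and the correlation of 0.6 are assumptions. Rising spread is plausible for antibodies because active gluten starts at Visit 2, but the SAP does not state it. Only secondary and exploratory analyses are touched. The point is worth correcting before unblinding, and it does not challenge the primary result.

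**What to change.** Name the time effect on the residual side in all six sets of models (anti-tTG, anti-DGP, BSFS, GSRS, CeD-GSRS, CeD PRO), for example `random time_r / residual subject=subjid type=UN;`. Here `time_r` is a CLASS copy of visit, week or day kept in chronological order.

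The copy matters. The existing reference-first coding sorts the earliest level last: the SAP's own contrasts put Visit 5 in column one and Visit 3 in column four. Using the existing variable would do no harm under UN but would misorder AR(1) and Toeplitz. In the daily CeD PRO model, day is continuous and not in CLASS, so a class copy of day is needed for the residual side, while day itself stays continuous in the fixed effects.

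The cost is a copied variable, a CLASS entry and one changed statement per model. The note in 7.6.1 allows this without an SAP amendment. A small-sample degrees-of-freedom method such as Kenward-Roger is a separate matter and does not repair this defect.

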RBC	Red blood cell
RCD-II	Type II Refractory Celiac Disease
RE	Role limitations due to emotional problems
SAE	Serious adverse event
SAP	Statistical analysis plan
SC	Subcutaneous
sCD3-	Surface CD3-negative
sCD8-	Surface CD8-negative
SD	Standard deviation
SOC	System organ class
ULOQ	Upper limit of quantification
UN	Unstructured
VT	Vitality
VH:CD	Villous height to crypt depth ratio

WBC White blood cell

WHO DD World Health Organization Drug Dictionary

1 Introduction

This is a statistical analysis plan (SAP) for study CELIM-NRCD-001 which is based on the final study protocol CELIM-NRCD-001 Version 3 (dated 29AUG2016). This SAP describes the statistical analyses which will be presented in the clinical study report.

2 Study objectives

The study objectives are the following:

The **primary objective** of the study is:

- To assess the efficacy of AMG 714 in attenuating the effects of gluten exposure in adults with celiac disease.

The **primary efficacy endpoint** is:

- Attenuation of gluten-induced small intestinal mucosal morphological injury, measured morphometrically as villous height to crypt depth (VH:CD) ratio.

The primary endpoint of the study is the difference in the Baseline-to-Week-12 % change of VH:CD ratio between each of the two AMG 714 dose arms against the placebo arm.

The **secondary efficacy endpoints** of the study are:

- Attenuation of gluten-induced small intestinal mucosal inflammation measured as intraepithelial lymphocyte (IELs) density;
- Attenuation of gluten-induced small intestinal mucosal morphological injury using a grouped classification of Marsh score;
- Attenuation of gluten-induced serum antibodies (i.e. anti-tissue transglutaminase antibodies [anti-tTG] IgA, anti-deamidated gliadin peptide antibodies [anti-DGP] IgA and IgG);
- Attenuation of gluten-induced clinical symptoms (i.e. Bristol Stool Form Scale [BSFS], Gastrointestinal Symptom Rating Scale [GSRS] and celiac disease GSRS [CeD-GSRS]).

The secondary endpoints of Marsh score and total IEL counts will be evaluated by the change from baseline to Week 12 between the two AMG 714 dose arms and the placebo arm. Anti-tTG IgA, anti-DGP IgA and IgG will be evaluated by comparing the change from baseline in results obtained after every four weeks of two AMG 714 dose arms and placebo arm. BSFS, GSRS and CeD-GSRS will be evaluated by comparing the change from baseline in weekly scores of two AMG 714 dose arms and placebo arm.

The **secondary objective** of the study is:

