  estimate "150 mg AMG 714 vs Placebo" trt 1 0 -1 /alpha=0.05 cl;
  estimate "300 mg AMG 714 vs Placebo" trt 0 1 -1 /alpha=0.05 cl;
  estimate "Visit 3: 150 mg AMG 714 vs Placebo" trt 1 0 -1
    trt*time 0 0 0 1
    0 0 0 0
    0 0 0 -1 /alpha=0.05 cl;
  estimate "Visit 3: 300 mg AMG 714 vs Placebo" trt 0 1 -1
    trt*time 0 0 0 0
    0 0 0 1
    0 0 0 -1 /alpha=0.05 cl;
  estimate "Visit 5: 150 mg AMG 714 vs Placebo" trt 1 0 -1
    trt*time 1 0 0 0
    0 0 0 0
    -1 0 0 0 /alpha=0.05 cl;
  ...
  estimate "Visit 8: 300 mg AMG 714 vs Placebo" trt 0 1 -1
    trt*time 0 0 0 0
    0 0 1 0
    0 0 -1 0 /alpha=0.05 cl;
  lsmeans trt /alpha=0.05 cl;
  lsmeans trt*time /alpha=0.05 cl;
  ods output CovParms=Cov_Par LSMeans=LS_est Estimates=Eff_est
    FitStatistics=Fit_Stat ParameterEstimates=Par_est
    Tests3=Type_3;
run;

```

Note that the value of `type` will be changed according to which covariance structure is being fitted.

The modelling results (parameter estimates, covariance parameter estimates, estimated treatment effect, marginal means estimates and results of the check of assumptions, e.g. the normality assumption) will be tabulated and 95% confidence intervals added, where appropriate. If the parametric assumptions are not met, then in addition to the above-specified model, a generalized estimating equation (GEE) approach will be used as well.

The baseline and post-baseline anti-DGP IgA and IgG results along with the change from baseline values will also be described by summary statistics and tabulated by treatment

group. Anti-DGP IgA and IgG results will also be listed. Individual and mean anti-DGP IgA and IgG results, will also be presented graphically by time point and treatment group.

PP populations will be used for the analysis.

Attenuation of gluten-induced clinical symptoms: Bristol Stool Form Scale (BSFS)

The Bristol Stool Form Scale is a pictorial aid to help subjects identify the shape and consistency of their bowel movements during the study (Riegler *et al* 2001).

Subjects will be asked to complete this form daily using an electronic diary at the time of each bowel movement from randomization through the Final Study Visit (Visit 8; Week 16/Day 112). If no bowel movements were experienced by the subject on any given day, the subject should document this using the electronic diary.

BSFS will be described by calculating daily and weekly number and type of bowel movements.

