    trt*week 0 0 0 0 0 0 0 0 0 0 0 0 0 0 0 0 0 0 1
    0 0 0 0 0 0 0 0 0 0 0 0 0 0 0 0 0 0 0
    0 0 0 0 0 0 0 0 0 0 0 0 0 0 0 0 0 0 -1
    /alpha=0.05 cl ilink;
  estimate "Week 0: 300 mg AMG 714 vs Placebo" trt 0 1 -1
    trt*week 0 0 0 0 0 0 0 0 0 0 0 0 0 0 0 0 0 0 0
    0 0 0 0 0 0 0 0 0 0 0 0 0 0 0 0 0 0 1
    0 0 0 0 0 0 0 0 0 0 0 0 0 0 0 0 0 0 -1
    /alpha=0.05 cl ilink;
  estimate "Week 1: 150 mg AMG 714 vs Placebo" trt 1 0 -1
    trt*week 1 0 0 0 0 0 0 0 0 0 0 0 0 0 0 0 0 0 0
    0 0 0 0 0 0 0 0 0 0 0 0 0 0 0 0 0 0 0
    -1 0 0 0 0 0 0 0 0 0 0 0 0 0 0 0 0 0 0
    /alpha=0.05 cl ilink;
  ...
  estimate "Week 16: 300 mg AMG 714 vs Placebo" trt 0 1 -1
    trt*week 0 0 0 0 0 0 0 0 0 0 0 0 0 0 0 0 0 1 0
    0 0 0 0 0 0 0 0 0 0 0 0 0 0 0 0 0 0 0
    0 0 0 0 0 0 0 0 0 0 0 0 0 0 0 0 0 0 -1 0
    /alpha=0.05 cl ilink;
  lsmeans trt /alpha=0.05 cl ilink;
  lsmeans trt*week /alpha=0.05 cl ilink;
  ods output CovParms=Cov_Par LSMeans=LS_est Estimates=Eff_est
    FitStatistics=Fit_Stat ParameterEstimates=Par_est
    Tests3=Type_3;
run;

```

Note that the value of `type` will be changed according to which covariance structure is being fitted.

The modelling results (parameter estimates, estimated ratio of the bowel movement rates in AMG 714 and placebo groups, estimated weekly ratios of the bowel movement rates in AMG 714 and placebo groups, marginal (i.e. least squares) means estimates and results of the check of assumptions, i.e. the over dispersion) will be tabulated and 95% confidence intervals added, where appropriate.

Weekly bowel movements and their BSFS types will be tabulated by treatment group and week and summarized by descriptive statistics, absolute numbers and percentages. Also, percentage of subjects with diarrhoea (at least 1 BSFS ≥ 6 for the week) and percentage of subjects with constipation (at least 3 days without bowel movement for the week) by week

and by treatment group will be presented. Individual and mean weekly bowel movement counts will also be presented graphically by time point and treatment group.

The daily bowel movement counts and their BSFS scores will only be listed.

PP populations will be used for the analysis.

Attenuation of gluten-induced clinical symptoms: Gastrointestinal Symptom Rating Scale (GSRS)

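### The only inferential BSFS analysis models total weekly bowel movements, without stool type or baseline adjustment, so it tests stool frequency and not the stool-form endpoint that SAP section 2 announces

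*SAP*

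**What the plan says.** Section 2 lists BSFS among the secondary endpoints for gluten-induced clinical symptoms and states how it will be assessed: "BSFS, GSRS and CeD-GSRS will be evaluated by comparing the change from baseline in weekly scores of two AMG 714 dose arms and placebo arm".

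Section 7.6.2 introduces the instrument as a "pictorial aid to help subjects identify the shape and consistency of their bowel movements". Subjects record it in an electronic diary at every movement. The section then specifies one model: "The total weekly bowel movement counts will be analysed using generalized linear mixed models with subject as a random effect". In the model definition, Y "is the total bowel movement count for subject" in a given week, with a Poisson distribution and log link. The fixed effects are treatment, sex, site, week and treatment by week. The week index runs from 0 to 16, and the SAS code contains treatment contrasts at Week 0. The effect reported is a ratio of bowel movement rates.

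Stool form appears only in descriptive output. Weekly types are tabulated by arm, the "percentage of subjects with diarrhoea (at least 1 BSFS ≥ 6 for the week") is presented alongside a constipation percentage, and daily scores are listed.

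**The concern.** The endpoint is named after a stool-form scale, but the model sees only how many movements occurred. A week of ten type 4 stools and a week of ten type 7 stools give the same response. The plan therefore specifies no test and no between-arm estimate for the property that the scale measures.

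There is also a plain mismatch inside the SAP. Section 2 announces change from baseline in a weekly score; the BSFS model uses neither a score nor a change, and has no baseline covariate. Section 7.2.1 defines Week 0 as the baseline for weekly scores, while the BSFS model treats Week 0 as an outcome week. The GSRS and CeD-GSRS models in the same section do use change from baseline with baseline adjustment.

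At stake is the inferential result for one secondary endpoint. If the mismatch stays, any stool-form test would have to be chosen after unblinding.

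**Working it through.** **The plan's own figure.** The SAP gives no power, rate or variance for BSFS. Its power statement (section 6) concerns VH:CD only; it is used here just to confirm 17 evaluable subjects per arm. With SD 36 and 48 error degrees of freedom, the noncentrality is 40 / (36 × √(2/17)) = 3.24 for 40 points and 35 / (36 × √(2/17)) = 2.83 for 35 points. Power is 88.8% and 79.3%, as stated.

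**Announced against specified.**

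| | Section 2 and 7.2.1 | BSFS model, 7.6.2 |
|---|---|---|
| Quantity | weekly BSFS score | total weekly movements |
| Contrast | change from baseline | rate over Weeks 0 to 16 |
| Baseline | Week 0 | no covariate; Week 0 is a response |
| Stool type | what the scale records | absent |

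The SAS response variable is named bsfs, but the text defines Y as the total count, so the name does not bring stool type in.

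**Structural result (equal totals).** Let each arm have mean μ movements per week, a share p of them type 6 or 7. The total-count ratio is μ/μ = 1.00 whatever p is. The loose-stool ratio is p(active)/p(placebo). With assumed shares of 10% and 30% it is 0.33.

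For μ = 7, the loose-stool means are 0.7 and 2.1 per week. For a single week with 17 per arm and pure Poisson variation:
- SE of the log ratio = √(1/(17 × 2.1) + 1/(17 × 0.7)) = 0.335
- |ln 0.333| / 0.335 − 1.96 = 1.32, so power is about 91%

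Overdispersion would lower the 91%. It would not move the 1.00.

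**Illustration with between-subject variation (all rates assumed).** There are 17 per arm and 10 gluten weeks. On drug, subjects have 7.5 formed and 1.5 loose stools a week; on placebo, gluten adds 2 loose stools a week. The between-subject log-SD is 0.35 (formed) and 0.8 (loose). The simulation uses 4000 replicates and a t-test on the log of each subject's mean weekly count, not the planned GLIMMIX model. Ratios are placebo over drug.

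| Placebo scenario | Total ratio | Type 6/7 ratio | Power, total | Power, type 6/7 |
|---|---|---|---|---|
| 2 loose stools, all extra | 11/9 = 1.22 | 3.5/1.5 = 2.33 | 31% | 79% |
| half replace formed | 10/9 = 1.11 | 2.33 | 10% | 80% |
| all replace formed | 9/9 = 1.00 | 2.33 | 5% | 80% |
| +1 loose, extra | 10/9 = 1.11 | 2.5/1.5 = 1.67 | 13% | 41% |
| +0.5 loose, extra | 9.5/9 = 1.06 | 2/1.5 = 1.33 | 7% | 15% |
| +2 loose, extra, loose log-SD 1.2 | 1.22 | 2.33 | 19% | 46% |

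The type 6/7 count does better in every row. In the last three rows neither response has adequate power.

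**The case against.** The strongest reply is that the plan is open about what it does. It says that both number and type of movements will be described, models number, labels the result a ratio of movement rates, and shows stool types and the weekly diarrhoea percentage by arm. Diarrhoea also enters other fitted models: questions 11, 12 and 14 are 3 of 15 GSRS items and 3 of 10 CeD-GSRS items, and diarrhoea and loose stool are 2 of 9 CeD PRO items. An effect on diarrhoea would therefore be visible in the report. That stands. But those items sit within totals on other instruments, so they do not test BSFS, and a table is not the between-arm comparison that section 2 promises.

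A second reply is that the power figures rest on one large assumed effect. That also stands; they are illustrative, and the last three rows of the table show how fast they fall. The 1.00 ratio under equal totals does not depend on them.

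A reader might also infer that gluten-induced diarrhoea and gluten-induced constipation cancel within the count. The SAP does not support this. It defines a constipation criterion but never calls constipation gluten-induced, and its celiac-specific CeD-GSRS leaves out all the constipation items (10, 13 and 15).

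**Conclusion.** The point holds as a specification fault. Section 2 and the BSFS part of section 7.6.2 disagree on the quantity, the contrast and the role of baseline, and the only inferential analysis tests stool frequency. Where loose stools replace formed ones, it has no treatment effect to detect at any sample size. Where loose stools are extra it has some sensitivity, and how much depends on rates that the SAP does not give.

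A reader might go further and infer that stool form is lost from the report, or that the trial cannot show an effect on diarrhoea. The descriptive tables and the diarrhoea items in the other questionnaires rule that out.

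This concerns one secondary endpoint of a Phase 2a trial and should be corrected; the VH:CD analysis is untouched.

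**What to change.** In the BSFS part of section 7.6.2:

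- Model the weekly number of movements with BSFS of 6 or more, over Weeks 1 to 16, with the Week 0 value as a covariate, to bring the model into line with section 2. State which days make up Week 0, because section 3 starts the diary at Visit 1, the day of the first dose.
- Alternatively, model the weekly diarrhoea indicator that the SAP already defines, with a logit link. It loses information when loose stools are common. In the equal-totals example (2.1 against 0.7 a week), the chance of at least one loose stool is 1 − exp(−2.1) = 0.88 against 1 − exp(−0.7) = 0.50, and single-week power is about 67%, against 91% for the count.
- State what happens if counts are overdispersed. The SAP only tabulates that check for BSFS. A negative binomial model would serve, or the GEE approach already planned for the other repeated-measures secondary endpoints.
- Keep the total count as a supportive analysis labelled stool frequency, and keep the descriptive constipation table.
- Amend section 2 so that its wording matches the chosen response.

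The cost is SAP text, one derived response and one covariate; no new data are needed. There are two drawbacks. Loose-stool counts are sparser and more variable than totals. The new response also measures diarrhoea, not the whole scale: type 1 and type 4 stools both count as zero. The unstructured starting covariance remains heavy, at 16 × 17 / 2 = 136 parameters for about 51 subjects, so the structured alternatives that the SAP lists will probably be needed.
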